## **Overview**

This will be the first study that aims to develop an Asian version of the clinically beneficial Mediterranean diet using ingredients commonly consumed in the Asian diet. With the developed AMD, we then aim to evaluate its acceptability among subjects with NAFLD. Despite numerous studies conducted using the Mediterranean diet in NAFLD, there is a paucity of information of the acceptability of Mediterranean diet among Asian patients with NAFLD. This can be attributed to the cultural differences in dietary habits between the western Mediterranean diet and the Asian cuisine. This study aims to reconstruct the traditional Mediterranean diet using Asian recipes and food preparation techniques and evaluate its acceptability in Asian subjects with NAFLD.

## **Study Protocol**

There will be 2 phases to this study:

### Phase 1 – Asian Mediterranean Diet Development

This phase of the study involves desktop research and recipe trials in SIT, and does not require IRB review as no human subjects are involved. We will ascertain the nutritional composition of the traditional Mediterranean diet by conducting a comprehensive literature review. This review will help us map out the portion sizes of foods commonly consumed in Mediterranean countries that adhere closely to this diet. Following this, we will identify substitute ingredients that are frequently consumed in the Asian diet. Subsequently, we will review the polyphenol studies and match the polyphenol content of both Mediterranean to Asian ingredients. The serving sizes of these ingredients will be determined based on this mapping. Using this information, we will develop a 4-week cycle menu for an Asian Mediterranean diet.

### Phase 2 – Sensory Evaluation Study

We will collaborate with a food catering company with SFA license to produce the recipes for 1 of the weeks in the 4-week cycle menu. Recipe trials will be conducted by the food company. Finalized recipes will be packaged as ready-to-eat meals for use in Phase 2 of our study.

## Study Population

We plan to recruit 30 adults diagnosed with NAFLD from the Department of Hepatology in Singapore General Hospital.

Inclusion criteria include:

- Diagnosis of NAFLD, as determined clinically by imaging evidence of hepatic steatosis on ultrasound/CT/MRI.
- Aged from 21 to 60 years old.

Exclusion criteria include:

- Secondary causes of NAFLD (e.g. medication-induced), unstable body weight (variation >5% within the preceding 3 months),
- Current use of weight loss medications,
- Other liver diseases (viral hepatitis, auto-immune or cholestatic liver disease, Wilson's disease, hemochromatosis, alpha-1 anti trypsin deficiency),
- Unstable diabetes (HbA1c >8.5%),
- Renal failure,
- Inability to provide informed consent,
- Pregnancy and lactation,
- Problems with tasting and smelling,
- Food allergy/intolerances/restrictions.

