## Study Visits Procedure

All eligible subjects will be given a participant information sheet and a consent form if they wish to participate in the study. The PI will also be available for any clarifications either through phone call or via email. With permission from the subjects, the SIT research team will message them to remind subjects of the requirements before coming for their study visits. Anthropometric data (weight, height, body mass index, waist circumference) and body composition using bioelectrical impedance will be assessed.

Recruited subjects will be invited to SIT@Dover campus tentatively in the months of Mar 2024 to Dec 2024 for two sessions of sensory evaluation test on the acceptability of the Asian Mediterranean diet (AMD) sample meals. All the ready meals will be heated up to

the required temperature before consumption. Subjects will taste a total of 14 different food items, over 2 study visits. This is to minimize taste fatigue if more than 5-7 samples are tasted at each study visit. After tasting the food items, subjects will be required to evaluate the food items tasted. A sensory evaluation form will be provided to the subjects. Subjects are required to complete the form before leaving the food tasting lab. The duration of each session is expected to take 60 minutes. Reimbursement will be given upon the completion of both study visits.

Sensory evaluation food tasting preparatory steps will involve:

1. All ready meals will be reheated to the appropriate consumption temperature when the subject arrives at SIT's food-tasting lab.
2. All trays, crockeries and cutlery will be provided. Environment settings will be standardised throughout all sessions.
3. Subject verification and registration will be carried out before subjects enter the food-tasting lab.
4. Before the commencement of the food-tasting session, subjects will be briefed on the food-tasting procedure and instructions.
5. A total of 7 food items will be served to participants and 50g of each food product will be portioned out. A pictorial illustration of the actual ready meal will be provided to the subject.
6. Subjects will be required to fill up the online food-tasting evaluation forms.
7. Throughout the tasting session, subjects will not be allowed to communicate with other subjects in the food-tasting lab.
8. Subjects will leave the food-tasting lab when they have finished evaluating all the food items.
9. Trays, crockeries, and cutlery will be collected back.

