#### Statistical Analysis Plan

As we are piloting the novel Asian Mediterranean diet, the primary objective is to obtain comments and feedback on the acceptability of the ready meals from NAFLD patients. The sensory data from this study were analysed using a Kruskal-Wallis test, and a one-

way analysis of variance (ANOVA) was used with significant differences detected for p <0.05.

Information about liver enzymes (ALT, AST, Albumin, bilirubin, alkaline phosphatase, and GGT), platelet count, and lipid profile (total cholesterol, LDL, HDL, TG) will be obtained from the subjects' medical records using the most recent laboratory data. Subjects will be required to complete a semi-quantitative food frequency questionnaire (FFQ) that includes foods and beverages commonly consumed in Singapore. The aim is to assess subjects' usual dietary intake over the past 6 months and evaluate their baseline dietary intake and adherence to the Mediterranean Diet.

Data collected by collaborators will be anonymized. Recruited participants will be de-identified through a subject ID to ensure the responses are kept anonymous. Participants' identifiable information like names, contact numbers, emails, gender, race, and age will be collected and stored securely in an encrypted password-protected file. Identity of participants will be kept in a separate file from the research data. Only the study investigators will have access to this file. The files containing all research data will be password-protected and stored in project PDDS folder. Access to data will be restricted to only authorised people who are involved in this study. The data will be retained in SIT for 10 years in line with SIT Research Data Management Policy Version 1.1.

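### Do the missing Asian-ethnicity criterion and the broad food-restriction exclusion leave the study population wrongly defined?

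*Combined protocol and SAP*

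**What the plan says.** The Overview states the aim twice. One sentence reads "we then aim to evaluate its acceptability among subjects with NAFLD". The closing sentence says the study will "evaluate its acceptability in Asian subjects with NAFLD". Between them the protocol notes how little is known about acceptability in Asian patients, and explains the gap: "This can be attributed to the cultural differences in dietary habits between the western Mediterranean diet and the Asian cuisine".

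Study Population reads: "We plan to recruit 30 adults diagnosed with NAFLD from the Department of Hepatology in Singapore General Hospital". It has two inclusion criteria (NAFLD on imaging, and age 21 to 60) and nine exclusion bullets. None mentions ethnicity. The last exclusion is "Food allergy/intolerances/restrictions", with no definition and no reference to the menu.

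Under Study Visits Procedure, "Subjects will taste a total of 14 different food items, over 2 study visits", seven at each visit. The Statistical Analysis Plan gives the primary objective as to "obtain comments and feedback on the acceptability of the ready meals from NAFLD patients", again without an ethnic qualifier. It lists race among the data collected and held in the identity file.

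**The concern.** Two things look wrong.

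The first is the population. The study exists because Asian and Mediterranean eating habits differ, so being Asian is central to the question. Yet the eligibility list would admit a non-Asian patient, and the primary objective does not say otherwise. A reader could ask to whom the acceptability result applies.

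The second is the food exclusion. Having to taste all 14 items is a reason to exclude someone who cannot eat one of them. It is not a reason to exclude someone whose restriction concerns a food that is never served. Because the term is undefined, different screeners might also apply it differently, and no count of patients excluded for this reason is planned. In a study about dietary culture, losing patients with restricted diets could narrow whose feedback is heard.

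What would be at stake is generalisability and consistency of screening. Every participant is to taste the same items, so a restriction on who enters does not favour one item over another within the sample.

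**Working it through.** **Population wording, section by section.**

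| Section | Population named | Ethnicity stated? |
|---|---|---|
| Overview, aim (second sentence) | Subjects with NAFLD | No |
| Overview, evidence gap | Asian patients with NAFLD | Yes |
| Overview, aim (closing sentence) | Asian subjects with NAFLD | Yes |
| Study Population | 30 adults with NAFLD, one hospital department | No (0 of 2 inclusion and 0 of 9 exclusion bullets) |
| Statistical Analysis Plan, objective | NAFLD patients | No |

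The difference in wording is real. However, the two aim statements sit in one short paragraph whose rationale and last sentence both say Asian, so the shorter forms read naturally as shorthand. It would be wrong to say that any NAFLD patient qualifies. Study Population also limits age, weight stability, weight-loss medication, other liver disease, diabetes control, renal function and more. The accurate statement is that there is no ethnicity requirement.

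**Does a number depend on it?** No. The target of 30 comes with no effect size, standard deviation, power or precision target, so there is no calculation that a different population label would alter.

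**The food exclusion.** That the wording excludes patients who could eat everything served cannot be shown. The items come from one week of a menu still to be developed, and no ingredients are listed. The most that can be said is that it may exclude such patients.

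**Screening losses, under assumptions.** Let *r* be the share of otherwise eligible patients with any restriction, and *q* the share of those whose restriction touches no served item. Neither is in the documents.

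- Turned away under the current wording while enrolling 30: 30*r*/(1 − *r*).
 - *r* = 0.1: 3/0.9 = 3.3
 - *r* = 0.2: 6/0.8 = 7.5
 - *r* = 0.3: 9/0.7 = 12.9
- Turned away if only restrictions touching a served item counted: replace *r* by *r*′ = *r*(1 − *q*).

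| | *r* = 0.1 | *r* = 0.2 | *r* = 0.3 |
|---|---|---|---|
| Current wording | 3.3 | 7.5 | 12.9 |
| *q* = 0.25 | 2.4 | 5.3 | 8.7 |
| *q* = 0.50 | 1.6 | 3.3 | 5.3 |
| *q* = 0.75 | 0.8 | 1.6 | 2.4 |

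These figures count extra screening only. They do not measure any shift in ratings or loss of representativeness, and they do not show that enrolling 30 is threatened.

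**Would the obvious changes help?**

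- *An Asian-ethnicity criterion.* The sections could be reconciled by adding the word or by dropping it, and nothing in the documents shows how many non-Asian patients might enrol at this one Singapore site. Race is already collected, so investigators with access to the identity file can supply aggregate counts without linking identities to ratings.
- *Limiting restrictions to served ingredients.* This would leave the same breadth in the allergy and intolerance exclusions. It could miss restrictions on how food is prepared or sourced. It also needs an ingredient list at screening. The Phase 2 section says "Finalized recipes will be packaged as ready-to-eat meals for use in Phase 2 of our study", but not that the recipes are final before patients are screened.
- *Defining the term, logging exclusions, using one label.* These write down detail that competent staff and authors would ordinarily supply. They change no comparison and no estimate.

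**The case for a change.** The strongest case for acting is that both gaps are visible on the page and cheap to close. Recruiting in Singapore probably makes most participants Asian, but it does not define the population. Race is collected, yet no eligibility rule or stated analysis uses it, so the documents make no commitment to tell the reader who was studied. The undefined restriction term invites uneven screening, and it bears on dietary culture, which is the study's premise. Tying that term to the menu need not expose anyone to a food they must avoid if the ingredient list is complete.

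Much of this stands as description: the labels differ, the term is loose, and a report that gives race and reasons for exclusion will be clearer than one that does not. What does not stand is the step to a change of plan. No harm to the results is shown, the number of patients affected is unknown in both cases, and the safety argument fails where a restriction concerns preparation or source and not an ingredient.

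**Conclusion.** No change follows. The population wording is a small inconsistency that the Overview's own rationale resolves and that analysts can handle by describing the sample with the race data already recorded. The blanket food exclusion is a fair trade-off: it may turn away some patients who could have taken part, in return for a simple rule in a 30-person pilot where everyone tastes all 14 items.

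The effect is confined to generalisability and screening consistency. Its direction and size cannot be determined from the documents, and the 3.3 to 12.9 patients turned away under the current wording rest wholly on assumed shares of 10% to 30%. The conclusion rests on three things: the study remains a pilot seeking feedback, recruitment stays at the one named department, and its conclusions are read as applying to patients who met the stated criteria. If the results were later used to claim acceptability across all Asian patients with NAFLD, including those with dietary restrictions, the eligibility criteria would not support that claim.

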## Study Visits Procedure

All eligible subjects will be given a participant information sheet and a consent form if they wish to participate in the study. The PI will also be available for any clarifications either through phone call or via email. With permission from the subjects, the SIT research team will message them to remind subjects of the requirements before coming for their study visits. Anthropometric data (weight, height, body mass index, waist circumference) and body composition using bioelectrical impedance will be assessed.

Recruited subjects will be invited to SIT@Dover campus tentatively in the months of Mar 2024 to Dec 2024 for two sessions of sensory evaluation test on the acceptability of the Asian Mediterranean diet (AMD) sample meals. All the ready meals will be heated up to

the required temperature before consumption. Subjects will taste a total of 14 different food items, over 2 study visits. This is to minimize taste fatigue if more than 5-7 samples are tasted at each study visit. After tasting the food items, subjects will be required to evaluate the food items tasted. A sensory evaluation form will be provided to the subjects. Subjects are required to complete the form before leaving the food tasting lab. The duration of each session is expected to take 60 minutes. Reimbursement will be given upon the completion of both study visits.

Sensory evaluation food tasting preparatory steps will involve:

1. All ready meals will be reheated to the appropriate consumption temperature when the subject arrives at SIT's food-tasting lab.
2. All trays, crockeries and cutlery will be provided. Environment settings will be standardised throughout all sessions.
3. Subject verification and registration will be carried out before subjects enter the food-tasting lab.
4. Before the commencement of the food-tasting session, subjects will be briefed on the food-tasting procedure and instructions.
5. A total of 7 food items will be served to participants and 50g of each food product will be portioned out. A pictorial illustration of the actual ready meal will be provided to the subject.
6. Subjects will be required to fill up the online food-tasting evaluation forms.
7. Throughout the tasting session, subjects will not be allowed to communicate with other subjects in the food-tasting lab.
8. Subjects will leave the food-tasting lab when they have finished evaluating all the food items.
9. Trays, crockeries, and cutlery will be collected back.

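### Serving order, the split of items over visits and the recording of position are left open, so item comparisons could carry position and visit effects that cannot be checked afterwards

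*Combined protocol and SAP*

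**What the plan says.** The combined protocol and SAP, under Study Visits Procedure, states: "Subjects will taste a total of 14 different food items, over 2 study visits". The reason given is "This is to minimize taste fatigue if more than 5-7 samples are tasted at each study visit". Step 5 of the numbered list adds: "A total of 7 food items will be served to participants and 50g of each food product will be portioned out". Step 2 standardises the environment, and step 6 says that "Subjects will be required to fill up the online food-tasting evaluation forms".

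On the timing of ratings, the narrative says "After tasting the food items, subjects will be required to evaluate the food items tasted". That wording fits rating each item in turn, and it also fits rating all 7 at the end.

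Neither the narrative nor the nine steps gives a serving order, a randomisation or counterbalancing scheme, a rule for allocating items to visits, or an instruction to record position.

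The Statistical Analysis Plan section makes comments and feedback on acceptability the primary objective of a pilot. It also states "The sensory data from this study were analysed using a Kruskal-Wallis test", together with a one-way ANOVA at p < 0.05. It does not name the grouping factor. Item is the natural reading.

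**The concern.** The plan accepts that ratings may change as tasting proceeds, and it limits each visit to 7 items for that reason. The limit reduces fatigue but does not spread what remains evenly over the items. Two ways of running the session are open, and each causes a difficulty:

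- **One order and one split for everybody.** Each item then has a fixed position and visit. A difference between items cannot be told apart from a difference between positions or visits, and recruiting more subjects does not help.
- **Items served together, with subjects choosing the order.** Any bias depends on how alike the chosen orders are. This cannot be examined, because position is not recorded.

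If each subject's order is independent and random, item means carry no position bias.

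The planned tests have no term for subject, position or visit, although every subject is to rate all 14 items. Any statement that one meal was better accepted than another rests on these comparisons.

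**Working it through.** **Inputs from the document.** 30 subjects (Study Population); 14 items, 2 visits and 7 items per session (Study Visits Procedure); Kruskal-Wallis and one-way ANOVA at p < 0.05 (Statistical Analysis Plan). The rating scale, SD, within-subject correlation and size of any drift are not given.

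**Step 1: the plan's own figure.** 14 / 2 = 7 items per visit, which agrees with step 5. There are 30 × 14 = 420 ratings and 14 × 13 / 2 = 91 item pairs. With two fixed sets of 7, 2 × (7 × 6 / 2) = 42 pairs lie within a set and 7 × 7 = 49 lie between sets.

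**Step 2: aliasing.** This needs no assumed SD or drift. Item has 14 − 1 = 13 df, within-visit position 6 and visit 1. The rank of the design matrix (subject, item, position, visit) gives:

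| Scheme | Position df added to item | Visit df added to item | Item df left after position and visit |
|---|---|---|---|
| Common order, common split | 0 | 0 | 13 − 6 − 1 = 6 |
| Random order within visit, common split | 6 | 0 | 13 − 1 = 12 |
| Random order, sets crossed over visits | 6 | 1 | 13 |

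In the first row the 6 remaining df are differences of differences between the two visits. No simple difference between two items is among them: the 42 within-set pairs differ in position and the 49 between-set pairs differ in visit. In the second row only the contrast between the two sets is lost. It touches the 49 between-set pairs and leaves the 42 within-set pairs clear.

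**Step 3: one illustration.** Assumptions, none from the document: 9-point scale, SD 1.8, within-subject correlation 0.3, 30 subjects, common order, linear drift of δ points per position, no true item difference.

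- Squared position deviations (positions 0 to 6): 9 + 4 + 1 + 0 + 1 + 4 + 9 = 28 per visit, 56 over two visits.
- Within-subject variance: 1.8² × 0.7 = 2.268.
- Noncentrality: 30 × δ² × 56 / 2.268, which is 7.4 at δ = 0.1 and 29.6 at δ = 0.2.
- The one-way ANOVA divides by a residual with expectation 1.8² = 3.24, because subject differences stay in it. With no drift its ratio centres near 2.268 / 3.24 = 0.70 instead of 1, so it is conservative.

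| Drift per position | ANOVA rejects | Kruskal-Wallis rejects |
|---|---|---|
| 0 | under 1% | under 1% |
| 0.05 | 1% | 1% |
| 0.1 | 8% | 7% |
| 0.15 | 36% | 33% |
| 0.2 | 80% | 76% |

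Sampling this F ratio directly with the correlation varied from 0.1 to 0.5, ANOVA rejects in 2% to 18% at δ = 0.1 and about 72% to 84% at δ = 0.2.

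**Step 4: why order and test belong together.** Under the same assumptions and a common order, a Friedman test rejects in about 29% at δ = 0.1 and 94% at δ = 0.2. Correcting the test alone would therefore turn more drift into apparent item differences. With random order and crossed sets, Friedman rejects in 4.3% to 5.1% over drifts of 0 to 0.2 and visit shifts of 0 or 0.5.

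For a real difference (one item 1.0 point higher, no drift), the planned ANOVA and Kruskal-Wallis detect it in about 21% and 18% of trials, against 49% for Friedman.

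**The case against.** **Nothing says a common order or split will be used.** A reader might infer that the item results will be biased. The document does not support that. The order could be set in the briefing (step 4) or the online form (step 6), neither of which is reproduced. This objection stands: the point is an uncontrolled design element.

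**The objective is feedback.** No ranking, selection rule or cut-off is stated, so an error in ordering the items has no defined consequence. This stands and lowers the priority. The section nevertheless plans significance tests on the sensory data.

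**The rejection rates are assumed.** This also stands. A 0.5-point visit shift gives ANOVA 18% under the values above, but 47% with a between-subject SD of 0.7 and a residual SD of 1.2. Below about 0.1 point per position the planned tests are little affected. The df results in step 2 do not depend on these values.

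**No later analysis could rescue a common order.** A reader might say this, but it is too flat. Six item df survive additive adjustment, and pairs within a set are free of visit effects under any split.

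**Later items may have cooled.** The plan says "All ready meals will be reheated to the appropriate consumption temperature when the subject arrives" and "The duration of each session is expected to take 60 minutes", which invites this inference. It does not say how much of the hour is tasting or whether food is kept hot, so no standing-time effect can be claimed.

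**Ignoring the subject is a separate defect.** True: it exists under any serving order. It is kept here because, as step 4 shows, the choice of test changes how strongly an order effect appears.

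**Conclusion.** The point holds as a gap in the design, with modest priority. The procedure names taste fatigue but leaves order, split and recording of position open, so it permits a session in which position and visit are aliased with item, or one in which their influence cannot be examined. Under a common order and split, 6 of 13 item df survive adjustment; under a common split alone, 12 of 13 do. These counts follow from the design. The rejection rates (under 1%, about 8% and about 80% at drifts of 0, 0.1 and 0.2) depend on the assumed scale, variance, correlation and linear drift, and on the natural but unstated reading that the tests compare items. The loss from ignoring the subject applies under any serving order; its size rests on the same assumed variances.

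**What to change.** **Study Visits Procedure.** Add: *At each visit the online form presents the 7 items in a random order generated for each subject. The subject tastes and rates each item before the next. Position and visit are stored with each rating.* Amend the narrative sentence on evaluating after tasting to match.

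Define two sets of 7 items, A and B. If both can be available across tasting days, assign 15 subjects at random to A then B and 15 to B then A. If not, state the fixed split and compare items only within each set.

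**Statistical Analysis Plan.** Name item as the factor compared. Replace Kruskal-Wallis and one-way ANOVA with a within-subject analysis: a mixed model with item, position and visit fixed and subject random, which keeps subjects who miss a visit, or a Friedman test on subjects with complete ratings.

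**Cost.** No extra subjects or visits. The random order and stored position use the online form already planned. Crossing the sets costs more, because both must be on hand across tasting days. Rating item by item must fit the session: 60 / 7 is about 8.6 minutes per item before allowing for the briefing.
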